Study protocol

Project title:

Preventing and approaching crises for frail community-dwelling patients through innovative care (PRACTIC) - an effectiveness study

Participatory action research in a cluster randomised controlled trial

This protocol represents **Work Package 2 (WP2)** in the PRACTIC-study (**Preventing and approaching crises for frail community-dwelling patients through innovative care**). The PRACTIC-study consist of four work packages:

WP1	Characteristics of crises in frail patients receiving home-care services
WP2	Evaluation of the effect of an adapted version of the TIME model in the prevention and treatment of crises in frail community-dwelling people
WP3	Pre-specified process-evaluation of the intervention in the RCT
WP4	Administration and project coordination

Abstract

Background:

Demographic changes, with an increasing number and proportion of older people with multimorbidity and frailty, will put more pressure on home care services in municipalities as well as on specialist health care. Frail multimorbid people receiving home care services are at risk of developing crisis often resulting in adverse events, coercive measures, and acute institutionalisation. Crises also pose increased demands and stress on the next of kin. There is a lack of evidence based interventions to prevent and resolve crises in community settings. Our hypothesis is that through interventions targeting the patients, the next of kin, the patients' social context, and healthcare service, crises may be prevented and resolved. This project aims to test the effectiveness of an adapted version of a bio-psychosocial person centred model the Targeted Interdisciplinary Model for Evaluation and Treatment of Neuropsychiatric Symptoms, (TIME) to prevent and resolve crises for frail community-dwelling people receiving home care services. In addition, we will analyse factors associated with the effect of TIME, and we will explore the experiences the users have with the introduction of TIME in the services.

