To evaluate the effects of a biopsychosocial intervention to prevent and resolve crises in a heterogeneous population, there is a need for a goal-oriented outcome comprising this variability. The goal of the intervention and the outcome will necessarily vary from patient to patient (26). We have therefore translated and modified a validated individual goal-oriented interview (The Bangor Goal-Setting Interview, BGSi) (34) to establish a common primary outcome to be used in the RCT. The PRACTIC Goal Setting Interview (PGSI) is a Norwegian adapted version of the BGSi. In the PGSI, the individual goals set for each patient represent treatment and actions targeting the challenges and symptoms that trigger and maintain the patient's crisis. The difference in goal achievement between the intervention and control groups, as further explained in the Methods section, defines our primary outcome.

Theoretical framework

The study is based on a theoretical framework of complexity science and a biopsychosocial understanding of crises (35, 36). In this framework, frailty means that the frail patient is prone to instability caused by complex interactions among biological, psychological and social stressors (14, 36). If this instability rises, it eventually culminates in the development of a crisis that, according to our description of crises, demands immediate and new actions. Describing frailty and crises as complex phenomena sets the stage for why interventions should be constructed and implemented as flexible complex interventions to be able to assess, prevent, and resolve crises (24). This also includes the choice of design and methods for testing the effectiveness of an intervention.

Aims and research questions

The primary purpose of this study is to test the effectiveness of an adapted version of a biopsychosocial person centred model (TIME) to prevent and resolve crises for frail community-dwelling people receiving home care services. We have formulated the following research questions:

RQ1: Can the TIME model adapted for home care service, prevent, and resolve crises in frail people receiving home care services?

RQ2: Which participant characteristics or organizational factors are associated with the effect of the TIME model?

RQ3: What are the experiences of the users of home care services on how crises were approached during the trial?

Design and methods

Study design

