For RQ1 we will use a participatory action research (PAR) design in a cluster randomized controlled trial (RCT) with two parallel groups: intervention municipalities (IMs) and control municipalities (CMs) (23, 37). Figure 1 shows a flow chart of the clusters and individuals through the phases of the trial based on the power calculation.

PAR aims to ensure adaptation of the components of the intervention to the local context (23, 37). This will be done by establishing a local project team in each municipality consisting of two representatives from the research group and local participants (representatives of local managers, staff, and GPs). These groups will adapt the implementation process and the TIME model according to the cyclic Deming process: plan, do, check, act, and adjust (38). The implementation process will be adapted to the local context to fit with the organizational structure already established in home care services. For example, the content and time used for educational and training purposes can vary depending on the educational level and established educational arenas. These variations will be registered during the process. For the TIME model, the core components (functional) of the intervention (TIME) must be fixed, and other components can be adapted to the local context and the patients included. An assessment phase must be performed, but *what* to assess and the *types* of clinical scales to be used can vary (processes). Case conferences using the inductive cognitive ABC model for the analyses of crises must be conducted, but the timeframe and participants of these conferences will vary. The action and evaluation phase must be conducted, but the timeframe and types of actions and evaluations can vary. These adaptations of the model will be accurately mapped in each setting during the study, and this mapping will be a part of the process evaluation study in the PRACTIC study (29). In this trial, we will follow the recommendations from the CONSORT

statement for randomized trials of nonpharmacologic treatments (39).

For RQ2 we will utilise an explorative design with multilevel regression analysis based on the participants' characteristics from the RCT and organizational data including staff characteristics from the process evaluation study in WP3.

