The proposed sample of 150 participants is based on a power calculation with clusters of approximately five participants from each of the 30 municipalities. Based on a previous trial, a minimal clinically important average difference on the PGSI scale is set to 2 points between intervention and control group with a standard deviation (SD) for change of 2.83 in each group (40). To observe a statistically significant difference with a power of 80%, an intra-cluster (municipality) correlation coefficient (ICC) of 10% and an estimated attrition rate of 25% for the primary outcome at three months, we will need approximately 150 participants. We assume a high attrition rate since the participants are at high risk for acute institutionalisation (see inclusion criteria).

This trial must perform cluster randomisation, with the municipality as the cluster, for two main reasons. The intervention is a biopsychosocial intervention that involves the entire interdisciplinary team and staff in the home care services of the participating municipalities to optimize the approach towards a group of patients in the municipalities. In addition, without cluster randomisation, the study runs the risk of transmitting all or parts of the intervention model to the individual control patients in the same municipalities (42). The patients in the control group will receive care and treatment as usual, but they will probably also profit from the extra attention given by the home care services because of their participation in the RCT and because of the use of the measure for the primary outcome, the PGSI. In this way, we can isolate any effects on goal achievements to prevent or resolve crises to the main difference between IMs and CMs, i.e., the TIME intervention.

RQ3 Selection of participants for the individual in-depth interviews

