Specially trained nurses (data assessors) from the project's research centre who are not affiliated with the municipalities will, together with staff members in the home care services, assess patients' baseline characteristics before randomisation. These data assessors will after randomisation be blinded to the randomisation result. They will assess the effect of the intervention via telephone by interviewing the participants, the next of kin and the staff members who know the patient best, at three months and six months after baseline assessments. All assessors are nurses with substantial experience and formal training on the use of the assessment scales. They will attend a one-day course on the use of the assessments scales before start of the trial. A description of the questionnaires, including data assessors, respondents and the time point(s) at which they are administered, is provided in Table 1.

Baseline data and primary and secondary outcome measures

The primary outcome of the trial is the difference in the change between the intervention and control groups in individual goal achievement to resolve or alleviate the challenges regarding crises between baseline and three months using the PGSI (scale of 1–10) (34). We chose this primary outcome because there is a need for a targeted outcome that comprises the variability in a heterogeneous population. It is very unlikely that a participant would be harmed due to participation in the RCT; therefore, it is not deemed necessary to have a harm outcome in the study. In the RCT, no new experimental treatments for the patients will be introduced, and care and all treatment actions will rely on recommended national care and treatment guidelines.

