Data describing the municipalities and the organization of the home care services will be assessed in the process-evaluation study part (WP3) of the PRACTIC project. To capture the care providers' adherence and fidelity to the adapted TIME model during the trial, members of the research team will contact one of the TIME administrators in each IM two times with two months interval during the trial to fill in a fidelity checklist with the four main components of TIME (i.e., the assessment phase, the performance of the case conferences, the actions taken and a systematic evaluations of these actions). This check-list will also capture any adaptations of the intervention and the TIME model done by the local project group. The checklist will be developed as a part of the PRACTIC process evaluation study in WP3.

Data collection for the qualitative data (RQ3)

The interviews will be based on a semi-structured interview guide where the participants will be asked to reflect on two main themes (58): 1) their experiences on how their health and care challenges were approached and eventually resolved during the trial and 2) their experiences in participating in shared decision-making about their care with the home care services and their GP. These main themes will be developed upon during the interview with open-ended and exploratory questions. When other key themes emerge spontaneously during the interviews, time will be allotted to elaborate these themes.

Data processing and statistical analysis of quantitative data for RQ1 and RQ2

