The data will be presented as frequencies and percentages for categorical and means (standard deviations) for the continuous variables. The normality of continuous variables will be assessed graphically. If necessary, skewed data will be transformed. Differences in the changes in outcomes between the intervention group and the control group will be assessed by a linear mixed model with fixed effects for time component and group and the interaction between the two. The analysis will be performed as an intention-to-treat analysis. A significant interaction will imply the differences in change between the groups. Random effects for patients nested within municipalities and slopes (if significant) will be included into the model. Individual time point contrasts will be derived within each group at each time point with the corresponding 95% confidence intervals and p-values. Linear mixed model correctly adjusts estimates for intra-cluster correlations as well as for intra-individual correlations due to repeated measurements in time. The model also handles unbalanced data by allowing inclusion of all available information, also from dropouts. The analyses for primary and secondary outcomes will be adjusted for baseline PGSI-scores, baseline severity of dementia (Clinical Dementia Rating), and age of the participants.

For RQ2 the dependent variables will be the changes from baseline in primary or secondary outcomes that are statistically significant after the implementation of TIME. Independent variables will be participants characteristics from the RCT, and organizational data (staff characteristics and organizational data) assessed in the process evaluation study in WP3.

Data analysis of qualitative data for RQ3

For the analysis, thematic content analysis will be used. Thematic content analysis is a method with the purpose to identify, analyse, and report patterns and themes in qualitative data (59, 60). The aim is to provide a systematic description of both the manifest and latent content of the data, and in the

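### RQ2 asks what is associated with the effect of TIME, but its stated regression of change on characteristics, with no arm-by-characteristic term, identifies predictors of change.

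*Protocol*

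**What the plan says.** The Abstract announces that "we will analyse factors associated with the effect of TIME", and RQ2 under Aims and research questions reads "Which participant characteristics or organizational factors are associated with the effect of the TIME model". Under Baseline data and primary and secondary outcome measures, the primary outcome is "the difference in the change between the intervention and control groups in individual goal achievement", so effect in this trial means a between-arm contrast.

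On method, Study design says that for RQ2 "we will utilise an explorative design with multilevel regression analysis". The section on data processing and statistical analysis for RQ1 and RQ2 gives the variables: "the dependent variables will be the changes from baseline in primary or secondary outcomes that are statistically significant after the implementation of TIME", and "Independent variables will be participants characteristics from the RCT, and organizational data" from the process evaluation. The only interaction in that section is group by time, in the RQ1 model. No RQ2 text says which arms are analysed.

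**The concern.** A factor is associated with the effect of TIME if the TIME-minus-control difference in change varies across its levels. A regression of change on the factor, without arm and its interaction, shows only who changes. The protocol itself expects change without TIME: of the control patients, the sample size section says "they will probably also profit from the extra attention given by the home care services because of their participation in the RCT".

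Two errors can follow. A factor that predicts change equally in both arms can be reported as marking who benefits from TIME. A true modifier can be missed or shown with the opposite sign. Municipalities could then be told, wrongly, which patients or services gain from the model.

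A lesser fault lies in the choice of outcomes. Restricting RQ2 to outcomes that reach significance is data-driven. It does not say whether a between-arm or a within-arm result counts, although the RQ1 model yields both. It also drops any outcome in which opposite subgroup effects cancel.

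**Working it through.** The protocol gives no figure for RQ2, so there is none to reproduce. The check is what the stated model estimates, followed by an illustration of size.

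**What is estimated.** Write change = a + b·arm + c·x + d·arm·x, with arm = 1 for TIME. RQ2 asks about d.
- TIME arm alone: the coefficient of x is c + d.
- Both arms pooled, equal sizes: the coefficient of x is about c + d/2.
- Neither equals d unless c happens to take a particular value. If d = 0, both return c.

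**Inputs from the protocol (sample size section).** 150 participants, 30 municipalities, 25% attrition, ICC 0.10, SD of change 2.83, target difference 2 points.
- Completers: 150 × 0.75 = 112.5, or about 56 per arm and 112.5/30 = 3.75 per municipality.
- Design effect: 1 + (3.75 − 1) × 0.10 = 1.275.

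**Assumptions not in the protocol.** Two-sided 5% level; correlation r between characteristic and change of 0.2, 0.3 or 0.4.

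**Case 1: same r in both arms, so no effect modification.** Probability of a flag = Φ(atanh(r)·√(n − 3) − 1.96). For r = 0.3 and n = 56: atanh(0.3) = 0.3095, times √53 = 7.280, gives 2.253; 2.253 − 1.96 = 0.293; Φ = 0.62.

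| Factor, sample | n used | r = 0.2 | r = 0.3 | r = 0.4 |
|---|---|---|---|---|
| Patient-level, TIME arm | 56 | 31% | 62% | 87% |
| Patient-level, pooled | 112 | 56% | 90% | 99% |
| Municipality-level, TIME arm | 56/1.275 = 43.9 | 25% | 51% | 77% |
| Municipality-level, pooled | 112/1.275 = 87.8 | 46% | 81% | 97% |

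The patient-level rows ignore clustering. A clustered simulation at r = 0.3 (30 municipalities of 3 to 4 completers, ICC 0.10, main effect 2 points, generalised least squares with the ICC known) gave 61% (TIME arm) and 89% (pooled) for a patient-level factor, and 42% and 72% for a municipality-level factor. The arm-by-characteristic term was flagged in 4 to 5%.

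**Case 2: a true patient-level modifier, r = 0.3 in controls and none under TIME.** Per SD of the factor, c = 0.3 × 2.83 = 0.85 and d = −0.85.
- TIME arm alone: c + d = 0, flagged in 5% of runs, so the modifier is missed.
- Pooled: c + d/2 = +0.42, the opposite sign to d. It is flagged in about 34 to 38% of runs, depending on simulation set-up, including whether an arm main effect is entered.
- Interaction model: centred on d, flagged in about 37% of runs.

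**Precision of an interaction estimate.** For a binary factor split evenly, there are four cells of 112.5/4 = 28.1, and SE = 2.83·√(4/28.1·f).
- Patient-level, f = 1 − 0.10 = 0.9: SE = 1.01; 95% CI half-width 1.96 × 1.01 ≈ 2.0; power for 2 points = Φ(2/1.01 − 1.96) ≈ 51%.
- Municipality-level, f = 1.275: SE = 1.21; half-width ≈ 2.4; power ≈ 38%.

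**The case against.** The strongest reply is that RQ2 gets only a sketch: no arms, random effects, adjustment or time point are named, and a statistical analysis plan, which is not at hand, could add arm and its interactions. RQ1 and RQ2 share one section, and the abstract says RQ2 uses the RCT data, which fits an extension of the RQ1 model to both arms. That reading is possible, but it is not written. The protocol does not defer the matter: it fixes a dependent variable and names the predictors, and following that text would not answer RQ2.

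It can also be said that RQ2 is exploratory. That excuses imprecision, not the estimation of a different quantity.

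Three points stand in part. First, the false-flag rates are in substance the power to detect a predictor of change; they show what would happen if such a factor exists, not that one does. Second, the interaction model is not powerful. If a factor acts only under TIME (r = 0.3 there, none in controls), the TIME-arm model flags it in about 65% of runs and the interaction model in only about 37%. But the TIME-arm model flags a factor that merely predicts change in both arms about as often, so it cannot tell the two apart. Third, confining exploration to outcomes that showed an effect is partly a matter of preference; the undefined meaning of significant is the firmer complaint.

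**Conclusion.** The concern holds. On either reading of the sample, the RQ2 model as written estimates predictors of change, not factors associated with the effect of TIME. The mismatch follows from the text and the algebra and needs no numerical assumption.

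Its size does rest on assumptions: for r between 0.2 and 0.4 in both arms, a factor that modifies nothing would be flagged in 25 to 87% of trials with the TIME arm alone, and in 46 to 99% with both arms pooled, against about 5% for an interaction term. The fault is confined to RQ2. It should be corrected before RQ2 is analysed.

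**What to change.** Name the RQ2 outcomes in advance, at least PGSI at 3 months adjusted for baseline PGSI, and analyse them whatever their significance in RQ1. Keep the planned multilevel regression, use patients of both arms, and include arm, characteristic and arm-by-characteristic terms. Report the interaction estimates with 95% confidence intervals, labelled exploratory.

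Factors recorded only in intervention municipalities cannot enter an interaction with arm. The fidelity checklist is one, since the research team will "contact one of the TIME administrators in each IM two times". Report these as within-arm associations with change. The alternative is to reword RQ2 as predictors of change.

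For patient characteristics the cost is wording only, because they are collected in both arms before randomisation. For organizational data the protocol does not say explicitly whether the process evaluation covers control municipalities; if it does not, those factors can only be within-arm associations. The price is the low precision shown above, which the report should state.

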Table 1. The assessment phase

Checklist for the assessment phase	
The following should be performed:	PRACTIC Goal Setting Interview (PGSI)
	Personal history and conversation with the person: what is the person's perspective? For example, "Who am I?"
	Medical history: A summary
	Somatic and psychological assessment and examination
	ADL assessment: Activities of daily living
	Nutritional screening
Suspected conditions:	 Yes  No If dementia is suspected, start a basic dementia assessment. In the case of known dementia, assess the degree of dementia.
	 Yes  No If pain is suspected, conduct a pain assessment.
	 Yes  No In the case of behavioral and psychological symptoms, map the symptoms.
	 Yes  No In case of nutritional difficulties, perform nutritional mapping.
	 Yes  No In case of acute confusion (delirium), map the symptoms and contact a doctor.
Agree upon a time and place for the case conference: TID administrator/manager	

Table 2. Agenda and timeframe for the case conferences

Agenda for guided reflection meeting (case conference), approximately 1 hour

Activity Preparation: Convene a meeting and prepare a meeting room with a blackboard or similar facilities (projector, if available). Check that a flip pad and markers are available. As many as possible from the home care service staff should attend the conference. The leading registered nurse and the GP should attend the conference, if possible.

1. Status Report: Personal history and main points from the patient's medical record are presented, 10 min. Decide in advance who should prepare and present the patient's personal history and the main points from the medical record.

2. Create a problem list, approximately 5 min.

3. Prioritize problems from the list, approximately 5 min.

4. Draw a five-column table on the whiteboard that includes facts – interpretations (thoughts) - emotions – actions – evaluation.

5. Describe facts from the registration and assessment phase one problem at a time, approximately 10 min.

6. Suggest interpretations – guided discovery – discuss and reflect on the interpretations, approximately 10 min.

7. Describe any emotions experienced by the staff with interpretations by the staff, approximately 10 min.

8. Suggest SMART (Specific, Measurable, Achievable, Relevant, Time-bound) actions based on the interpretations and decide how and when to perform an evaluation of the actions, approximately 10 min.

9. Summarize interpretations and actions and close the meeting, approximately 5 min.
